The last interval, referred to as "end of study" in [Table 3-1](#), will include data available within the last 4 weeks prior to study treatment discontinuation plus 30 days or cut-off date, whichever comes first. When a patient discontinues data will be reported in the "end of study" time window as well as the one corresponding to the assessment (e.g., a patient discontinued treatment at week 58 data will be reported in the key point 52 weeks interval and in the "end of study").

In instances where more than one measure is reported in the time window associated with a key time-point (e.g., at 12 weeks), the measurement taken closest to the key-time point will be considered in the analysis. If two measures were taken on dates that are equidistant from the key time-point (e.g., 12 weeks - 5 days and 12 weeks + 5 days following the index date), the measure associated with a more severe condition (e.g., larger non-target lesion volume, higher pain severity score, lower functional assessment score) will be considered.

In instances where both a non-missing value and a missing or unknown value are reported in the time window associated with a key time-point, only the non-missing value will be considered in the analysis.

Similar rules applies to the volumetric measurement available for the patients.

If a patient has more than one volumetric measurement available for a single target lesion in the time window associated with the index date (i.e., up to 24 weeks prior to the index date) or at 24 weeks (i.e., ± 4 weeks) following the index date, the measurement taken closest to the index date or 24 weeks following the index date will be considered in the analysis. If two volumetric measurements for a single target lesion were taken on dates that are equidistant from the index date or 24 weeks following the index date, the larger of the two measurements (i.e., greatest volume) will be considered. All measurements available will be listed.

Imputation rules for the dates are reported in the [Appendix](#).

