For the Wong Baker scale, “improvement” is defined as a decrease by at least 2 points and worsening is defined as an increase by at least 2 points. For the FLACC and the Numerical scales, an “improvement” is defined as a decrease by at least 1 point and worsening is defined as an increase by at least 1 point. Results from other scales will be listed, if reported.

To further assess pain reduction at week 24 time point the following items will be summarized at index date and between week 24 or 6 months (+/- 4 weeks): concomitant medications used for pain excluding opioids; opioids; medical conditions/treatment emergent adverse events (by grade) related to pain; pain score from the questionnaire. A pain reduction will be flagged if improvement is reported for at least one of the following items provided that none of the other items is associated with a deterioration during the same period: pain score from the questionnaire, number of concomitant medications excluding opioids, number of opioids, number and severity of pain related medical conditions/treatment emergent adverse events.

To identify concomitant medications used for pain the following ATC will be selected:

1. M02 "TOPICAL PRODUCTS FOR JOINT AND MUSCULAR PAIN";
2. M03 "MUSCLE RELAXANTS";
3. N02 "ANALGESICS";
4. V10B PAIN PALLIATION";
5. M09AB01 "chymopapain".

To identify concomitant opioids used for pain the ATC code N02A "Opioids" will be used.

Current medical conditions/adverse events related to pain will be identified by selecting all Preferred Terms (PT) related to pain. The list of PT used to select pain will be identified by the clinical team and archived.

Table 3-5 Endpoints related to objective #6

Measure	Type of variable	Summary Statistics	Timing
Proportion of patients with symptom/complication/comorbidity overall and by severity	Binary	Frequency, percentage	At key time-points
Type of symptom/complication overall and by severity	Categorical	Frequency, percentage	At key time-points
Proportion of patients with “High”, “Medium” and “Low” impact symptoms/complications/comorbidities adverse events (see definition in section 3.6 Secondary endpoints) by primary	Categorical	Frequency, percentage	Overall

Measure	Type of variable	Summary Statistics	Timing
system organ class (SOC) and preferred term (PT)			
Proportion of patients with a pain assessment performed	Binary	Frequency, percentage	At index date

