Proportion of patients with improvement, worsening and stable in pain severity	Binary	Frequency, percentage	At key time-points
Pain reduction (indicator)	Binary	Frequency, percentage	At week 24 time-point

Endpoints related to secondary objective #7: Change in functional status

The following endpoints are included for analysis to describe any improvement in PROS patients being able to return to, or improve their attendance at work/school, as well as any change in their ability to undertake usual activities of daily living, such as improvements in mobility. It is anticipated that the data availability associated with these endpoints may not be consistent across all patients/sites; however it will be reported as available and utilized also to generate physician narratives.

The number of patients attending work/school/pre-school will be summarized at the index date and the percentage of patients reporting improvement, worsening or stable at each time-point will be reported. The reason for change of status will be listed where available.

Frequency counts and percentages will be presented for mobility assessments at the index date and at key time-points. Performance status scores (ECOG, Lansky, Karnofsky) will be reported appropriately by age category, at the index date and the percentage of patients reporting improvement, worsening or stable in score will be summarized at baseline, 12, 24 and 52 weeks windows as well as the "End of study".

For work attendance:

- "Improvement" is defined as a shift from reporting of "No attendance" to "Part-time" or "Full time", from "Part-time" to "Full-time", as well as from "Unemployed" to "Part-time" or "Full-time" work.
- "Worsening" is defined as a shift from reporting of "Part-time" to "No attendance", "Full-time" to "Part-time" or "No attendance" as well as "Part-time" or "Full-time" to "Unemployed" status.

Similarly, for school attendance:

- "Improvement" is defined as a shift from reporting of "No attendance" to "Part-time" as well as, "Part-time" or "No attendance" to "Full-time";
- "Worsening" is defined as a shift from reporting of "Part-time" to "No attendance", as well as from "Full-time" to "Part-time" or "No attendance".

Work attendance will only be reported for the adult patients (i.e., ≥ 18 years of age) while school attendance will be reported for both pediatric and adult patients

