4.1 General definitions

Study treatment

The term study treatment or study drug will be used in this document and will refer to alpelisib.

Date of first administration of study drug

The date of first administration of alpelisib is defined as the first date when a non-zero dose of alpelisib is administered and recorded in the (e)CRF. This date is referred to as index date and used as reference start date.

Date of last administration of study drug

The date of last administration of alpelisib is defined as is the last date when a nonzero dose of alpelisib is administered and recorded in the (e)CRF.

Study day

The study day, describes the day of the event or assessment date, relative to the reference start date. The study day is defined as:

- The date of the event (visit date, onset date of an event, assessment date etc.) – reference start date + 1 if event is on or after the reference start date;
- The date of the event (visit date, onset date of an event, assessment date etc.) – reference start date if event precedes the reference start date.

Time unit

A year length is defined as 365.25 days. A month length is 30.4375 days (365.25/12). If duration is reported in months, duration in days will be divided by 30.4375. If duration is reported in years, duration in days will be divided by 365.25.

Baseline

For safety and efficacy evaluations, the last available assessment on or before the date of start of alpelisib is defined as “baseline” assessment.

On-treatment assessment/event and observation periods

For adverse event reporting the overall observation period will be divided into two mutually exclusive segments:

1. *pre-index date/pre-treatment period*: from up to 24 weeks prior to the index date through to the day prior to the index date.
2. *post-index date/on-treatment period*: from date of first administration of study treatment to 30 days after date of last administration of alpelisib (including start and stop date).

Safety summaries (tables, figures) include only data from the on-treatment period with the exception of baseline data which will also be summarized where appropriate (e.g. change from baseline summaries).

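### The Week 24 pain-reduction composite is reported in the favourable direction only, so in this single-arm study its rate cannot be told apart from fluctuation

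*SAP*

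**What the plan says.** SAP section 3.6, secondary objective #6, names the items that feed the composite: "pain score from the questionnaire, number of concomitant medications excluding opioids, number of opioids, number and severity of pain related medical conditions/treatment emergent adverse events". The rule has two parts. One improving item is enough to raise the flag: "A pain reduction will be flagged if improvement is reported for at least one of the following items". There is also a safeguard: "provided that none of the other items is associated with a deterioration during the same period".

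On timing, the items are to be "summarized at index date and between week 24 or 6 months (+/- 4 weeks"). SAP Table 3-1 sets the Week 24 window at 20 up to, but not including, 32 weeks. Where several measures fall in one window, SAP section 3.3 says that "the measurement taken closest to the key-time point will be considered in the analysis". SAP section 4.1 takes as baseline "the last available assessment on or before the date of start of alpelisib is defined as" the baseline assessment.

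On reporting, Table 3-5 has one row for the composite, a binary pain-reduction indicator at the Week 24 time point. The same table reports the questionnaire score as improvement, worsening and stable. Table 3-6 does the same for attendance and for ECOG, Karnofsky and Lansky. SAP section 3.6.1 makes all secondary analyses descriptive.

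**The concern.** The composite counts patients who moved in the good direction and does not count those who would meet the mirrored rule. Pain scores, drug counts and pain-related conditions all vary over half a year without any treatment effect. A rule that any one of four such items can satisfy will flag some patients even if nothing has truly changed. With no control arm and no worsening rate beside it, the reader has nothing to set the percentage against.

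SAP section 3.6 says the objective #6 endpoints are there to link efficacy on the primary endpoint with improvement in symptoms. Protocol section 6.8.1 describes overall efficacy from the primary and secondary endpoints together, and protocol section 9 foresees submission to health authorities. A bare percentage of patients with pain reduction is likely to be read as benefit.

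**Working it through.** The plan states no rate, sample size or precision for this composite, so there is no figure of its own to reproduce.

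**Inputs from the documents.** Four items; the flag needs at least one improvement and no deterioration on the others (SAP section 3.6). Window length: 32 − 20 = 12 weeks (SAP Table 3-1).

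**Assumed, not in the documents.** With no true change, each item improves with probability p and worsens with probability p, independently of the others.

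**Step 1: flag rate with no true change.** No item worsens with probability (1−p)^4. No item moves at all with probability (1−2p)^4. So P(flag) = (1−p)^4 − (1−2p)^4.

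| p | (1−p)^4 | (1−2p)^4 | P(flag) | Without the safeguard, 1−(1−p)^4 |
|---|---|---|---|---|
| 0.02 | 0.922 | 0.849 | 7.3% | 7.8% |
| 0.05 | 0.815 | 0.656 | 15.8% | 18.5% |
| 0.10 | 0.656 | 0.410 | about 25% | 34.4% |
| 0.20 | 0.410 | 0.130 | 28.0% | 59.0% |

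The safeguard does real work, and more of it as the items get noisier. Under these assumptions the mirrored worsening flag has the same rate, so improved minus worsened has expectation zero.

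**Step 2: how far the assumptions matter.**
- Correlated items (common correlation 0 to 0.6, p from 0.05 to 0.20, simulated): 13% to 37%.
- Items already at zero. A patient on no opioids, no other analgesics and with no pain-related condition can improve only on the score. The rate is then p(1−p)^3: 0.05 × 0.857 = 4%, 0.10 × 0.729 = 7%, 0.20 × 0.512 = 10%.
- Unequal chances. With 15% improving and 10% worsening per item, as regression to the mean could produce, the flag is 0.90^4 − 0.75^4 = 0.656 − 0.316 = 34%. The mirror is 0.85^4 − 0.75^4 = 0.522 − 0.316 = 21%.

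**Step 3: one date against a window.** Twelve weeks can collect more drugs and pain events than one day, and treatment-emergent events exist only after the index date. That makes worsening likelier on the three count items. Let q be their chance of worsening, with p = 0.10 elsewhere. Then P(flag) = (1−p)(1−q)^3 − (1−2p)(1−p−q)^3 and P(mirror) = (1−p)^4 − (1−2p)(1−p−q)^3.
- q = 0.20: flag 0.461 − 0.274 = 18.6%; mirror 0.656 − 0.274 = 38.2%.
- q = 0.30: flag 0.309 − 0.173 = 13.6%; mirror 0.656 − 0.173 = 48.3%.

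A simulation of steady-state episodes points the same way (assumed mean episode length 12 or 52 weeks; score chance 0.1 to 0.3 each way). Date against date gives a flag of 23% to 31%, with the mirror equal to it up to simulation error. Date against the whole window gives a flag of 6% to 25% and a mirror of 35% to 53%.

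**The case against.** The strongest reply is that worsening of pain is largely visible elsewhere. The score is reported both ways at 12, 24 and 52 weeks and at end of study, the components are themselves to be summarised at both times, and symptoms are reported by severity. The safeguard already removes patients with mixed movement, and the lack of a comparator is common to every endpoint in this descriptive study. All of this is true. It limits the harm, but none of it gives the composite rate its own counterpart, and the composite is the figure most easily quoted.

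Four stronger readings are tempting, and the documents do not support them.
- *The unequal periods inflate the flag.* Step 3 shows the opposite tendency. For the pain score, the closest-measurement rule already sets one value against one value. One pull the other way exists: Table 4-1 can move a partly missing start date to the treatment start date and so raise the index count. It touches partial dates only, and its size is unknown.
- *Chance is shown to produce a sizeable rate.* The documents give no per-item rates. At p = 0.02 the figure is about 7%, and it is lower still for patients with items at zero.
- *Every other measure is reported three ways.* Mobility is reported by severity level.
- *Equal look-back and look-forward intervals would solve the timing.* Treatment-emergent events cannot occur before the index date, and protocol section 6.1 promises only such pre-index information as is available.

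**Conclusion.** The point holds as a low-cost improvement to a descriptive secondary measure. The composite is one-directional, unlike the pain score, attendance and performance status, and with no control arm its rate cannot be separated from fluctuation. Under an assumed symmetric chance of change of 2%, 5%, 10% or 20% per item each way, with four independent items, about 7%, 16%, 25% or 28% of patients would be flagged with no true change. These figures illustrate the rule and do not predict this cohort.

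The date-against-window comparison is a separate and smaller flaw. For drug and condition counts it is not like for like, and it would tend to hide improvement. The SAP does not say how those counts are taken over the window, so the extent cannot be fixed from the documents. The primary endpoint is unaffected.

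**What to change.** Report the composite in four exclusive categories:
- improved: the rule as it stands;
- worsened: at least one item deteriorates and none of the others improves;
- mixed: items move both ways;
- stable: no item moves.

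Give improved minus worsened. For drug and condition counts, compare status at a single date on both sides, the index date and the date of the Week 24 assessment, in place of a date against a window. In the same paragraph, state what change in a count or in severity is improvement or deterioration, how many items a patient needs, and the denominator. The SAP is silent on these.

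The cost is a few table rows and a derivation rule, with no new data. The difference cancels symmetric fluctuation only. Regression to the mean would remain: in the 15% and 10% illustration the difference is still 34% − 21% = 13 points. A footnote should say so.

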For alpelisib a dose reduction is defined as a decrease in dose from the starting dose (e.g. from 250 mg daily to 200 mg daily) even if the dose decrease has been directly preceded by an interruption. On the other hand, if the dose decrease is followed by an interruption, with the dose resuming at the same level prior to the interruption (e.g. in the sequence 250 mg daily – 0 mg - 250 mg daily), the second dose decrease or change in dosing frequency will not be counted as dose reduction.

An interruption is defined as a zero dose on one or more days between two non-zero doses.

A dose increase is defined as an increase as compared to the starting dose level. Note that a dose rechallenge i.e when a patient goes back to the previous prescribed dose after an interruption, is not considered as an increase.

Table 3-4 Endpoints related to objective #5

Measure	Type of variable	Summary Statistics	Timing
Duration of exposure to alpelisib	Continuous	N, mean, median, standard deviation, Q1, Q3, minimum and maximum	Overall during study period
Alpelisib average daily dose; cumulative dose; dose intensity; relative dose intensity	Continuous	N, mean, median, standard deviation, Q1, Q3, minimum and maximum	Overall during study period
Proportion of patients that discontinued alpelisib	Binary	Frequency, percentage	Overall during study period;
Reason for discontinuation of alpelisib	Categorical	Frequency, percentage	Overall during study period;
Proportion of patients with an alpelisib dose adjustment	Binary	Frequency, percentage	Overall during study period
Proportion of patients with an alpelisib dose interruption	Binary	Frequency, percentage	Overall during study period
Reason for alpelisib dose interruption	Categorical	Frequency, percentage	Overall during study period

Measure	Type of variable	Summary Statistics	Timing
Number of alpelisib dose interruptions and/ or discontinuations	Continuous	N, mean, median, standard deviation, Q1, Q3, minimum and maximum	Overall during study period
Proportion of patients receiving PROS-related medication	Binary	Frequency, percentage	Overall during study period; At key time points
Indication of treatment for PROS-related medication	Categorical	Frequency, percentage	Overall during study period; At key time points
Proportion of patients receiving non-drug treatment by type (e.g., feeding tube, ketogenic diet)	Categorical	Frequency, percentage	Overall during study period;

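### The ATC list behind the Week 24 pain-reduction indicator omits M01, so drugs coded only to M01 are not counted and some substitutions are misread

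*SAP*

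**What the plan says.** SAP 3.6, under secondary objective #6, defines a yes/no pain-reduction indicator at Week 24 or 6 months. Table 3-5 reports it as a frequency and percentage. It has four items: "pain score from the questionnaire, number of concomitant medications excluding opioids, number of opioids", and the number and severity of pain-related conditions or adverse events. A patient is flagged when at least one item improves and none of the others deteriorates.

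Pain drugs are found by code: "To identify concomitant medications used for pain the following ATC will be selected". Five entries follow:

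- M02, "TOPICAL PRODUCTS FOR JOINT AND MUSCULAR PAIN"
- M03, muscle relaxants
- N02, analgesics
- "V10B PAIN PALLIATION"
- M09AB01, the single substance chymopapain

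Opioids are the N02A subset. The list is closed: it is not introduced as examples, and recorded indication is not used as a second route in. M01 appears nowhere in the protocol or SAP.

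Under objective #5, the SAP says that concomitant medications are coded with a WHO drug dictionary that uses the ATC classification. Table 3-4 also has a row "Indication of treatment for PROS-related medication", so indication is summarised for that class of drugs. The pain indicator does not use it.

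**The concern.** The list reaches as far as topical products, muscle relaxants and one named substance, but skips the group that holds systemic anti-inflammatory drugs. Because the item is a count, leaving out a group does more than lose information. A switch across the edge of the list looks like a drug gained or lost when the number of pain drugs has not changed. The flag rule then turns that into an improvement or a veto.

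The pain score will not always settle the matter. Table 3-5 itself tabulates how many patients had a pain assessment at the index date, and Protocol 6.3 warns that some variables will be unavailable for some patients. Where there is no score, the drug counts can decide the flag. Where there is one, a spurious deterioration in a count can cancel a real improvement.

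At stake is one of the measures meant to show symptomatic benefit. Protocol 6.8.1 describes overall efficacy from the primary and secondary endpoints together, and Protocol 9 says the results are intended as primary data for health authorities.

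**Working it through.** The plan gives no figure to reproduce. The check applies the SAP's own rule.

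**Inputs.** The five ATC entries, N02A for opioids, the four items and the flag rule all come from SAP 3.6. The meaning of M01 is a definition in the ATC system that the SAP adopts; the documents do not print it.

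**Step 1: does the list reach M01?** Matching by code prefix, an M01 code (M01AE01) fits none of the five entries. An N02B code (N02BE01) fits N02.

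**Step 2: the rule.** An item improves if its Week 24 count is below its index count, and deteriorates if above. Flag = at least one item improved and none deteriorated. Pain events are held unchanged, and so is the pain score except where stated.

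| Change from index to Week 24 | SAP list | With M01 added |
|---|---|---|
| Listed non-opioid → M01 drug | improvement; flag yes | no change; flag no |
| Opioid → M01 drug | opioid item improves; flag yes | non-opioid item deteriorates; flag no |
| M01 drug stopped | no change; flag no | improvement; flag yes |
| M01 drug → listed non-opioid | deterioration; flag no | no change; flag no |
| Same, with pain score improved | flag no | flag yes |
| M01 drug started | no change; flag no | deterioration; flag no |
| Same, with pain score improved | flag yes | flag no |

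**Step 3: all patterns.** Take one opioid, one listed non-opioid and one M01 drug, each used or not at index and at Week 24: 2^6 = 64 patterns, with score and pain events unchanged.

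- Flag present with the SAP list, absent with M01 added: 4.
- Flag absent with the SAP list, present with M01 added: 5.
- Total changed: 4 + 5 = 9 of 64.
- M01 use itself changes in 64/2 = 32 patterns. All 9 lie among these, so in 32 − 9 = 23 of them the flag is the same under either list.

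These are logical patterns, not expected numbers of patients.

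**Step 4: scale.** One wrong flag moves the proportion by 1/n. The documents do not give n for this indicator: SAP 3.6.2 uses patients with data at the time point. For orientation only, 1/50 = 2.0 percentage points at the 50 patients of Protocol 6.6, and 1/65 = 1.5 points at the 65 expected to be eligible.

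**The case against.** The strongest reply is that this is one count inside one descriptive flag, and that the SAP shows the underlying data elsewhere. All concomitant medications are summarised by ATC class and preferred term. Indication is tabulated for PROS-related medication. The components of the flag are summarised separately at index and Week 24, and pain severity has its own improvement, worsening and stable categories. All of this is true. It limits the harm but does not correct the flag, which is reported as a result in its own right.

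A second reply is that the content of M01 is not in the documents, and that a drug carrying several ATC codes might enter through a listed one. The first half is answered by the SAP's choice of the ATC system. The second half stands: the SAP does not say whether one code or all codes are searched, so the point is secure only for drugs coded solely to M01.

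A reader might go further in three ways that the documents do not support:

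- **Changes in anti-inflammatory use are wholly invisible.** They are missed only by the medication-count item. The pain score and pain-event items can still move.
- **The error equals the share of patients whose M01 use changes.** Step 3 shows otherwise. Starting an M01 drug, or swapping one for a listed analgesic, gives no flag under either list unless another item improves. Errors also run in both directions and can partly cancel. Any assumed share of patients changing use, multiplied by points per patient, would have no basis in the documents.
- **Drugs should be included or excluded by recorded indication as the main rule.** The SAP shows indication only for PROS-related medication, and Protocol 6.9 expects incomplete charts. A fixed code rule at least works the same way at both time points.

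**Conclusion.** The point holds. Following the SAP as written, drugs coded only to M01 are left out of the non-opioid count, and the flag is wrong for some patterns of use: false reductions when an M01 drug replaces a listed analgesic or an opioid, and missed reductions when an M01 drug is stopped or replaced by a listed analgesic. Adding M01 changes the flag in 9 of 64 logical patterns, 4 one way and 5 the other, so no net direction of bias can be claimed.

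The effect on the reported percentage cannot be computed, because the documents give neither use of these drugs nor the denominator. The conclusion assumes the standard ATC meaning of M01 and no entry through a second listed code. It concerns one descriptive secondary indicator. The primary endpoint, its Clopper-Pearson interval and the precision table do not depend on it.

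**What to change.** In SAP 3.6, objective #6:

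1. Add M01 (at least M01A) to the ATC list for non-opioid pain medication.
2. State whether one or all ATC codes per drug are searched.
3. Apply the same rule at index and at Week 24 or 6 months.
4. Report the indicator with and without M01. The current definition then stays visible, which matters because the SAP is already a final addendum dated 07-Jul-2021.
5. Use recorded indication at most for a supplementary analysis, where it is available.

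The cost is a short SAP edit, a programming change and one extra row of output, since concomitant medications are already to be ATC-coded. The downside is that some M01 drugs taken for fever or inflammation will be counted as pain medication; showing both versions lets the reader see how much that matters. If M01 was left out on purpose, the SAP should give the reason.
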